**Confidential**

---

- Suggests that the research places subjects or others at greater risk of harm (including physical, psychological, economic, or social harm).

## **10.2 Subject Information and Informed Consent**

The investigator is responsible for obtaining written informed consent from each individual participating in this study after adequate explanation in layman's terms regarding the nature of the study, along with the aims, methods, objectives, and any potential risks. The informed consent form must be appropriately signed and dated by the subject or the subject's legally authorized representative and the person obtaining the consent (if required by the IRB/IEC) prior to conducting/obtaining any study-related assessments including the discontinuation of any medications prohibited for the study.

If the informed consent form is amended during the study, the investigator must follow all applicable regulatory requirements pertaining to approval of the amended informed consent form by the IRB/IEC and use of the amended document (including for ongoing subjects).

The informed consent form shall also contain the subject's authorization for the use and disclosure of his/her protected health information (PHI) in connection with the study. The authorization shall include at a minimum a clear description of the following: the duration of the authorization, the subject's right of access to the PHI (or any suspension thereof during the course of the study), type of information to be used/disclosed in the study, the names or classes of parties that may use or disclose the PHI, the purpose of the use/disclosure of PHI, the extent of the subject's right to revoke the authorization, the extent to which participation in the study is conditioned on signing the authorization, and the potential for re-disclosure of PHI.

The original and any amended signed and dated informed consent forms must be retained at the study site; and a copy must be given to the subject or subject's legally authorized representative(s).

## **10.3 Study and Site Closure or Discontinuation**

Upon completion of the study, the following activities, when applicable, must be conducted by the monitor in conjunction with the investigator, as appropriate:

- Return of all study data to Salix (or designee).
- Data clarifications and/or resolutions.
- Accounting, reconciliation, and final disposition of used and unused study drug and placebo.
- Review of site study records for completeness.

**Confidential**

---

In addition, Salix reserves the right to temporarily suspend or prematurely discontinue this study either at a single site or at all sites at any time and for any reason. If such action is taken, Salix will discuss this with the investigator (including the reasons for taking such action) at that time. Salix will promptly inform all other investigators and/or institutions conducting the study if the study is suspended or terminated for safety reasons, and will also inform the regulatory authorities of the suspension or termination of the study and the reason(s) for the action. If required by applicable regulations, the investigator must inform the IRB/IEC promptly and provide the reason for the suspension or termination.

#### **10.3.1 Study Discontinuation**

Should the investigator, Salix, the FDA or local regulatory authorities become aware of conditions arising during the conduct of this study that may warrant the cessation of the study, such action may be taken. Prior to such action, consultation between Salix, the investigator, and, as appropriate, the FDA and/or local regulatory authorities will take place. Conditions that may result in the termination of the study or parts thereof include, but are not limited to, the following:

- The discovery of an unexpected, serious, or unacceptable risk to the subjects enrolled in the study
- A decision on the part of Salix to alter, suspend, or discontinue the development of the investigational product

#### **10.3.2 Study Site Discontinuation**

The study site can be discontinued at the request of Salix, the investigator, or by the FDA or local regulatory authorities.

Conditions that may warrant discontinuation of the study site include, but are not limited to, any of the following:

- Failure of the investigator to accrue subjects into the study at an acceptable rate.
- Failure of the investigator to comply with GCPs and/or applicable current regulations.
- Submission of knowingly false information from the research facility to the sponsor, FDA, or other regulatory authorities.
- Insufficient adherence to protocol requirements and procedures.

If the study is prematurely discontinued, all study data must be returned to Salix or designee. In addition, the site must conduct final disposition of all used and unused study drugs in accordance with Salix procedures for the study. Study termination and follow-up will be performed in compliance with GCP and applicable regulations.

Confidential

---

Financial compensation to investigators and/or institutions will be in accordance with the agreement established between the investigator and Salix.

#### **10.4 Handling and Record Keeping**

##### **10.4.1 Case Report Forms and Database Processing**

Subject data will be collected in an electronic CRF using Electronic Data Capture (EDC). The EDC system will be Part 11 compliant and will have a documented audit trail for all changes made to the electronic CRF.

The Investigator or designee must enter all required subject data using the specified data collection method defined by Salix. The Investigator must sign and date a declaration on the electronic CRF attesting to his/her responsibility for the quality of all data entered and that the data represents a complete and accurate record of each subject's participation in the study. Electronic case report form data will be provided to the Investigator at the end of the study and will need to be retained by the Investigator.

##### **10.4.2 Source Documents**

Source documents consist of, but are not limited to, in-patient hospital charts, clinic notes, out-patient records, original test results, laboratory data, worksheets, drug accountability records, informed consent forms, etc. Source documents must be available for review and inspection during on-site monitoring of the study by Salix, their designees, IRB/IEC, and/or appropriate regulatory authorities.

##### **10.4.3 Subject Tracking**

A drug accountability log, subject identification log (to be retained by the investigator only), and subject screening/enrollment log will be used to track subject participation in the study.

##### **10.4.4 Study Files**

The investigational center will maintain a special study file. This file is subject to review and inspection as described under Section 9.2 and Section 9.3 of this protocol.

##### **10.4.5 Data Management**

Data management will be performed in accordance with the standard operating procedures of Salix or its designee.

#### **10.5 Confidentiality**

Anonymity of subjects participating in this study will be maintained. Only subject initials and subject number will be on any study documents submitted to the sponsor. Every effort will be

**Confidential**

---

made to maintain the confidentiality of documents that identify the subject by name (e.g., signed informed consent document, laboratory reports, clinic charts), except to the extent necessary to allow auditing by the FDA, or other regulatory authorities. Should the name and/or address of a subject participating in this trial be on a document submitted to the FDA, or other regulatory authorities (e.g., laboratory report), the name and/or address will be completely blocked out and replaced with the subject initials and number.

The investigator and other study site personnel will keep confidential any information provided by Salix (including this protocol) related to this study and all data and records generated in the course of conducting the study, and will not use the information, data, or records for any purpose other than conducting the study. These restrictions do not apply to: (1) information which becomes publicly available through no fault of the investigator or study site personnel; (2) information which it is necessary to disclose in confidence to an IRB/IEC solely for the evaluation of the study; (3) information which it is necessary to disclose in order to provide appropriate medical care to a study subject, or (4) study results which may be published as described in Section 10.8. If a written contract for the conduct of the study which includes confidentiality provisions inconsistent with this statement is executed, that contract's confidentiality provisions shall apply rather than this statement.

## **10.6 Record Retention**

Essential documents as described above should be retained for one of the following time periods:

- At least 2 years after approval of the last marketing application,

***OR***

- At least 2 years have elapsed since the formal discontinuation of clinical development of the investigational product.

These documents should be retained for a longer period however if required by applicable regulatory requirements (i.e., local or country-specific regulations) or by an agreement with the sponsor. It is the responsibility of Salix to inform the investigator/institution as to when these documents no longer need to be retained. It is the investigator responsibility to notify Salix if they move or retire so that document storage can be addressed.

## **10.7 Financing and Insurance**

### **10.7.1 Finance**

The study is supported by Salix.

Confidential

---

### **10.7.2 Insurance and Indemnification**

Documentation of product liability insurance is on file at Salix and is available upon request.

### **10.8 Publication Policy**

An Institution and/or the investigator shall have the right, consistent with academic standards, to publish or present the results of the study, provided such publication or presentation does not disclose confidential information or other proprietary trade secrets of Salix. Salix will work with the protocol development team to identify a lead author for manuscript development. The manuscript authors will be determined by the amount of effort and participation each investigator contributes towards the study design, the conduct of the study and the analysis of the study data. Prior to any publication, presentation or other disclosure, the institution and/or investigator will submit the manuscript of any proposed publication (including abstracts, or presentation to a journal, editor, meeting, seminar, or other third party) to Salix at least sixty (60) days before publication, and Salix shall have the right to review and comment upon the proposed publication. Upon sponsor's request, publication will be delayed up to ninety (90) additional days to enable Salix to secure adequate intellectual property protection of property of Salix that could be affected by said publication. Salix shall have the right to require the deletion of any trade secret, or proprietary or confidential information of sponsor. Any publication or disclosure by the Institution and/or Investigator shall give appropriate credit to Sponsor. Where title is not retained by the publisher, title to and the right to determine the disposition of any copyrightable material, first produced or composed in the performance of the study, shall remain with the Institution and/or investigator. With respect to such materials, the Institution and/or investigator hereby grants to Salix an irrevocable, royalty-free, nonexclusive right to reproduce, translate, and use any such copyrighted material for its own research and commercial purposes. Investigator acknowledges and agrees that the study data and results may be disclosed by Salix to other clinical investigators, the FDA, and other regulatory authorities.

### **10.9 Ownership**

All data and records provided by Salix or generated during the study (other than a subject's medical records) and all inventions discovered during the course of conducting the study are the property of Salix. If a written agreement is executed by the parties for the conduct of the study, which includes ownership provisions inconsistent with this statement, the ownership provisions contained in the written agreement between the parties shall control.

**APPENDIX 1: OVERALL TIME AND EVENTS SCHEDULE**

| STUDY ASSESSMENTS  | Screening Period               | Treatment Period                  |                         |                      |   |                      |                | Follow-Up Period                           | Unscheduled Visit |
|--|--------------------------------|-----------------------------------|-------------------------|----------------------|---|----------------------|----------------|--|-------------------|
|  |                                | Visit 2                           | Visit 3, 4, 5, 6        | Visit 7              | Visit 8, 9, 10, 11, 12, 13, 14, 15,             | Visit 16 (EOT)       | Visit 17 (EOS) |  |                   |
| Study Visit  | Visit 1                        |                                   |                         |                      |   |                      |                |  |                   |
| Study Week   |                                | 0                                 | 2, 4, 8 and 12          | 16                   | 20, 24, 28, 32, 36, 40, 44, 48                  | 52                   | 54             |  |                   |
| Study Day  | -21 to -14                     | 1                                 | 14, 28, 56, 84
(±3d) | 112 (±3d)            | 140, 168, 196, 224, 252, 280, 308, 336
(±3d) | 364 (±3d)            | 378 (±3d)      |  |                   |
| Informed Consent   | X                              |                                   |                         |                      |   |                      |                |  |                   |
| Assign Subject Identification                              | X                              |                                   |                         |                      |   |                      |                |  |                   |
| Medical History and Demographics                           | X                              |                                   |                         |                      |   |                      |                |  |                   |
| Adverse Events and Concomitant Medications                 | X                              | X                                 | X                       | X                    | X   | X                    | X              | X  |                   |
| Inclusion/Exclusion Criteria                               | X                              | X                                 |                         |                      |   |                      |                |  |                   |
| Vital Signs, Weight, and Physical Examination a | X (includes height) | X                                 | X                       | X                    | X   | X                    | X              | X (Vital Signs and Weight Only) | X                 |
| Electrocardiogram  | X (duplicate)       |                                   |                         | X                    |   |                      | X              | X  |                   |
| Pregnancy Test   | X (serum)           | X (urine)              |                         | X (urine) | X (urine) (V10 and V13 only)         | X (serum) |                |  |                   |
| Safety Laboratory Tests b                       | X                              | X                                 | X                       | X                    | X   | X                    | X              | X  | X                 |
| Blood Sample for Inflammatory Markers and PXR (V2 only)    |                                | X                                 |                         | X                    |   | X                    |                |  |                   |
| Pharmacokinetic Blood Sample                               |                                | X                                 | X (V6 only)             |                      | X (V15 only)                                    |                      |                |  |                   |
| Stool Collection and Processing                            | X                              |                                   |                         | X                    |   |                      | X              |  |                   |
| Stool/Blood for Long-term Storage                          |                                | X                                 |                         | X                    |   |                      | X              |  |                   |
| CDAI assessment calculated by EDC                          | X                              |                                   | X                       | X                    | X   |                      | X              |  |                   |
| Ileocolonoscopy (SES-CD) c                      | X                              |                                   |                         | X                    |   |                      | X              |  |                   |
| IBDQ and WPAI-CD   |                                | X                                 |                         | X                    | X (V10 and V13 only)                            |                      | X              |  |                   |
| Electronic Daily Diary Instructions/Completion             | X                              | X                                 | X                       | X                    | X   |                      | X              |  |                   |
| Randomization  |                                | X                                 |                         |                      |   |                      |                |  |                   |
| Dispense Study Drug  |                                | X (1st dose at clinic) | X (except V3)           | X                    | X   |                      |                |  |                   |
| Study Drug Collection/Compliance                           |                                |                                   | X                       | X                    | X   | X                    |                |  |                   |

- a. Perform a full physical examination at Screening (Visit 1), prior to the Long Term Treatment Phase (Visit 7), and at End of Treatment (Visit 16); perform disease and symptom driven physical examination (including assessments for abdominal mass and extraintestinal manifestations of Crohn's disease based on CDAI – see Appendix 2) at other visits.
- b. Including *C. difficile* safety testing as described in Section 6.3.5
- c. The baseline ileocolonoscopy will be performed between Day -12 and Day -5; it will provide the baseline SES-CD, and will be used to assess Inclusion Criterion #3. Bowel prep will be dispensed at Visit 1. Ileocolonoscopy to be completed within 7 days after Visit 7 and Visit 16. Bowel prep will be dispensed at Visit 7 and Visit 16, cleansing regimen to begin after Visit 7 and Visit 16 assessments.

Confidential

**APPENDIX 2: CROHN'S DISEASE ACTIVITY INDEX (CDAI)**

| DAY   | -7   | -6                       | -5                       | -4                       | -3                       | -2                       | -1                       | 7 day Total  |
|---|--|--------------------------|--------------------------|--------------------------|--------------------------|--------------------------|--------------------------|--|
| 1. Number of liquid or very soft stools*  |    |  |  |  |  |  |  |  X 2 =   |
| 2. Abdominal pain   |    |  |  |  |  |  |  |  X 5 =   |
| 0 = none, 1 = mild, 2 = moderate, 3 = severe                                      |  |                          |                          |                          |                          |                          |                          |  |
| 3. General well being   |    |  |  |  |  |  |  |  X 7 =   |
| 0 = generally well, 1 = slightly under par, 2 = poor, 3 = very poor, 4 = terrible |  |                          |                          |                          |                          |                          |                          |  |
| 4. Extraintestinal manifestations subject has now (check ALL that apply)   |  |                          |                          |                          |                          |                          |                          |  |
| Arthritis/arthritis   |    |                          |                          |                          |                          |                          |                          |  |
| Iritis/uveitis  |    |                          |                          |                          |                          |                          |                          |  |
| Erythema nodosum/ pyoderma gangrenosum/ aphthous stomatitis                       |    |                          |                          |                          |                          |                          |                          |  |
| Anal fissure, fistula or abscess  |    |                          |                          |                          |                          |                          |                          |  |
| Other fistula   |    |                          |                          |                          |                          |                          |                          |  |
| Fever over 37.8°C (100°F) during past week  |    |                          |                          |                          |                          |                          |                          |  |
| Total checked boxes   |  |                          |                          |                          |                          |                          |                          |  |
| 5. Antidiarrheal drugs in the last 7 days                                  |  No = 0, Yes = 1   |                          |                          |                          |                          |                          |                          |  X 20 =  |
| 6. Abdominal Mass   |  None = 0, Questionable = 2, Definite = 5  |                          |                          |                          |                          |                          |                          |  X 30 =  |
| 7. Hematocrit (% rounded to whole number)   | Male 47 -
or Female 42 -  = 
If negative, enter 0 |                          |                          |                          |                          |                          |                          |  X 6 =   |
| 8. Body Weight Calculation**  |  |                          |                          |                          |                          |                          |                          |  |
| Ideal Weight  |  kg  |                          |                          |                          |                          |                          |                          |  |
| minus Actual Weight   |  kg  |                          |                          |                          |                          |                          |                          |  |
| =   |  ÷ Ideal Weight =  X 100 =             |                          |                          |                          |                          |                          |                          |  |
| (rounded to whole number****)  |  |                          |                          |                          |                          |                          |                          |  |
| TOTAL CDAI =    |  |                          |                          |                          |                          |                          |                          |  |

\*Graded using the Bristol Stool Form Scale (Appendix 3)

\*\* See Appendix 8 for calculations of Ideal Body Weight

\*\*\*\* If calculated value >-10, record -10 (maximum lower limit)

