#### **6.2.1 Crohn's Disease Activity Index (CDAI) Score**

The CDAI score is a weighted, composite index of eight items (stool frequency, severity of abdominal pain, degree of general well-being, presence or absence of extraintestinal manifestations including fistula, use or non-use of antidiarrheal agents, presence or absence of abdominal mass, hematocrit and body weight). Scores range from 0 to approximately 600 with higher scores indicating greater disease severity. Clinical (asymptomatic) remission is defined as a score of  $\leq$  150 points. Mild-to-moderate disease and severe disease are defined by scores of  $>$  150 to  $\leq$  450, and  $>$  450 points, respectively. The CDAI scoring system can be found in Appendix 2: Crohn's Disease Activity Index. CDAI will be evaluated at all clinic visits for the study. CDAI score will be calculated by EDC system.

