7.7.2 Secondary Efficacy Analysis

7.7.2.1 Binary outcomes

Analysis of binary endpoints will be based on the methods outlined above for the primary efficacy analysis. It includes:

- Induction of clinical remission defined as a CDAI Score of less than 150 points at Week 16.
- Clinical symptom remission over time: The total number of liquid/very soft stools for the 7 days prior to each clinic visit being ≤ 10 ; AND (2) an abdominal pain rating of ≤ 1 on each day for the last 7 days prior to each clinic visit in $\geq 80\%$ of the study visits during the 52-Week Treatment Period, including Week 52.
- Proportion of subjects with response to the abdominal pain component of the co-primary endpoint at post-baseline time points.

- Proportion of subjects with response to the liquid/very soft stool component of the co-primary endpoint at post-baseline time points.
- Proportion of subjects with SES-CD score of 0 at Week 52.
- Proportion of subjects who achieve clinical remission by the CDAI endpoint at post-baseline time points.
- Percentage of subjects who achieve clinical response at post-baseline time points.
Clinical response is defined as a reduction of at least 100 points from the baseline CDAI score.

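### The limit on CDAI item 8 (body weight) in Protocol Appendix 2 is printed with its inequality reversed; scored as written, it lowers CDAI for almost any weight other than about 110% of ideal

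*Protocol*

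**What the plan says.** Protocol Appendix 2 builds item 8 in steps: ideal weight "minus Actual Weight", divided by ideal weight, times 100, "rounded to whole number". Unlike the stool, pain, hematocrit and other weighted items, it shows no further multiplier, so one percentage point is one CDAI point. Ideal weight comes from a table: "See Appendix 8 for calculations of Ideal Body Weight". The footnote on the rounded value is "If calculated value >-10, record -10 (maximum lower limit").

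Item 7 (hematocrit), on the same form, has its own lower bound: "If negative, enter 0".

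Protocol 6.2.1 states that higher scores mean more severe disease and that "CDAI score will be calculated by EDC system". Neither document shows that system's formula, and neither restates the limit on item 8 anywhere else.

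The total CDAI is used for eligibility (220 to 450, Protocol 4.1) and for several secondary endpoints. The first of these is "Induction of clinical remission defined as a CDAI Score of less than 150 points at Week 16" (SAP 7.7.2.1; also Protocol 2.2.3). Others are remission at post-baseline time points, a fall of at least 100 points, time to remission and time to loss of response (Protocol 2.2.3, SAP 7.7.2.4).

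**The concern.** Item 8 is positive for an underweight subject and negative for an overweight one. A lower limit of -10 should replace values that are more negative than -10. The printed sign replaces values that are less negative, including zero and every positive value, and leaves the very negative ones alone. -10 then becomes the highest possible score for the item. Body weight could never add a point to CDAI, although Protocol 1.1 lists weight loss among the symptoms of the disease.

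This is an operative scoring rule. Someone programming the EDC calculation from Appendix 2 has only this footnote for the limit. A score that is too low moves subjects across fixed cut-offs. At follow-up, remission is called too readily and too early, and loss of response is called too late. At screening, a subject just above 220 could be excluded and one just above 450 admitted.

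**Working it through.** **Inputs.** Formula, rounding and limit: Protocol Appendix 2. Ideal weights: Protocol Appendix 8. Cut-offs: Protocol 4.1 and 2.2.3.

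**Definitions.** v = round(100 × (ideal − actual) / ideal).
- Printed rule: score −10 if v > −10, otherwise v.
- Floor rule: score −10 if v < −10, otherwise v.

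**Step 1: does the printed rule reproduce the stated lower limit of −10?** Run over v = −100 to +40:
- Printed rule: highest score −10, lowest −100. The stated limit is not reproduced; −10 is the maximum.
- Floor rule: lowest score −10, highest +40. The stated limit is reproduced.

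Only the floor rule agrees with the words in the parenthesis and with the direction of the bound on item 7.

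**Step 2: size of the error (printed minus floor).**
- v > −10: error = −10 − v = −(v + 10)
- v = −10: error = 0
- v < −10: error = v − (−10) = v + 10

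The error is never upward. Example from Appendix 8: a man of 175.3 cm, ideal weight 69.8 kg.

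| Actual kg | v | Printed | Floor | Error |
|---|---|---|---|---|
| 55.8 | +20 | −10 | +20 | −30 |
| 62.8 | +10 | −10 | +10 | −20 |
| 69.8 | 0 | −10 | 0 | −10 |
| 76.8 | −10 | −10 | −10 | 0 |
| 83.8 | −20 | −20 | −10 | −10 |
| 97.7 | −40 | −40 | −10 | −30 |
| 104.7 | −50 | −50 | −10 | −40 |
| 115 | −65 | −65 | −10 | −55 |

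**Step 3: effect at a cut-off.** With ideal 70 kg and actual 63 kg, v = 100 × 7/70 = +10 and the error is −20. A CDAI of 165 would read 145, below 150.

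**Step 4: who is set to −10.** v > −10 means an actual weight below about 1.10 × ideal. With the Appendix 8 tables this is a BMI of about 23 to 27, depending on height and sex (about 25 for a man of 175.3 cm or a woman of 160 cm). The documents give no weight or BMI distribution. Purely as an assumption, normal BMI distributions with cut-offs of 24 to 26 give these shares:

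| Assumed BMI mean (SD) | Share scored −10 |
|---|---|
| 22 (4) | 69–84% |
| 24 (4.5) | 50–67% |
| 25 (5) | 42–58% |
| 27 (6) | 31–43% |

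**Step 5: the 100-point response.** At stable weight the same error enters baseline and follow-up and cancels in the difference. It does not cancel if weight changes. If the man above went from 55.8 to 62.8 kg, the floor rule would give a 10-point fall (20 to 10). The printed rule would give none (−10 to −10).

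**Step 6: the main endpoints.** The co-primary and key co-secondary endpoints (Protocol 2.2.1 and 2.2.2, SAP 4.1 and 4.2) use CDAI items 1 and 2 and the SES-CD. Item 8 enters none of them.

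**The case against.** The strongest reply is that the meaning is plain from the same line. A limit called a lower limit is a floor, and the printed sign can be read as loose shorthand for further out than −10. The literal reading makes the calculation box pointless for anyone not more than 10% overweight, so a programmer would probably have noticed. The score is computed in a system whose code is not in the documents, so no score has been shown to be wrong. This stands, and it is why the point is minor. It does not remove the contradiction, because nothing else in either document settles it.

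It is also fair that one character carries the whole point, so the sign should first be checked against the approved protocol.

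Several stronger readings are tempting but unsupported:
- A reader might infer that nearly every subject would be scored −10. Step 4 shows that this depends on a weight distribution that the documents do not give.
- A reader might take 30 points as the largest error. It is the error at two particular weights; the table goes to 55.
- A reader might assume that underweight is frequent in this population. Protocol 1.1 names weight loss as a symptom but gives no frequency.
- A reader might infer a biased treatment comparison. The same rule applies to both arms, and no differential effect has been shown.
- A reader might extend the problem to the primary analysis. Only enrolment could carry it there.

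Finally, both studies are to be terminated early (SAP 7.3), and the secondary endpoints become descriptive if the primary endpoints are not significant (SAP 7.7.2.4). That lowers the stakes. The SAP nevertheless keeps the CDAI endpoints, so the scores will still be reported.

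**Conclusion.** The rule is wrong as written, and the matter is minor. That the sign contradicts its own label and the item's sign convention is certain on the printed text. Its effect on the data is unknown and is nil if the EDC system applies a floor.

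If the printed sign was followed, the errors are those in the table: always downward, and zero only where the rounded value is exactly −10. They would bear on CDAI eligibility, on remission defined as CDAI below 150, on time to CDAI remission and on time to loss of response. The 100-point response would be largely spared at stable weight. These sizes rest only on the Appendix 2 formula and the Appendix 8 weights. The shares in Step 4 rest on assumed BMI distributions and should not be quoted as estimates for this trial.

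**What to change.** 1. Reconcile the inequality in the Appendix 2 footnote with its label. The label supports recording −10 when the calculated value is below −10. This changes one character.
2. Confirm the item 8 formula in the EDC specification, with test values on both sides of the limit; v = +20, 0, −10 and −40 are enough. Under a floor they return 20, 0, −10 and −10. Under the printed rule they return −10, −10, −10 and −40.
3. If the EDC system used a floor, state that in the study report; nothing else is needed.
4. If it followed the printed sign, recompute item 8 and CDAI before the analysis. Weight is measured at each clinic visit and height at Visit 1 (Protocol 6.3.8), and Appendix 8 supplies ideal weight, so no new data are required. Report how many enrolled subjects had a screening CDAI that crosses 220 or 450 on recomputation, because enrolment cannot be undone.

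Steps 1 to 3 cost almost nothing. Step 4 is one derivation program.
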